1.0 SUMMARY

We are interested in measuring the frailty of older blood cancer patients with precision, determining how much it contributes to prognosis compared with clinical disease-specific measures, and determining if co-management by a geriatrician embedded in the oncology clinic can improve outcomes. We thus propose to characterize the prognostic value of frailty as compared to clinical prognostic models for older patients with blood cancers, and, using a randomized design, determine if co-management of frail older adults with blood cancers by an embedded geriatrician reduces frailty and/or improves outcomes such as survival and non-scheduled hospital admissions.

2.0 BACKGROUND/RATIONALE

2.1 Overview

The Institute of Medicine (IOM) defines patient-centered treatment as “care that is respectful of and responsive to individual patient preferences, needs, and values.”¹ Given the explosion in diagnostic and treatment options and the aging of the US population, this focus is arguably nowhere more important than in cancer care for the elderly. In their recent report, “Delivering High-Quality Cancer Care: Charting a New Course for a System in Crisis,” the IOM made recommendations for older cancer patients, whose population is poised to double in less than two decades.² The report describes the complexity of caring for older adults with cancer, as they have multiple chronic conditions, decreased cognition, may need assistance in activities of daily living, and may be more vulnerable to treatment side effects. The biology of their cancers is also often different, as it may result from—or interact with—age-related somatic mutations not seen in younger patients. Recommendations for this coming “crisis” included using “evidence-based care parameters” as the basis for medical decisions. This seems a tall order, given that there are sparse data to inform care for this population.

Aging is the result of the accumulation of molecular and cellular damage over time, eventually leading to a loss of this physiological reserve across many organ systems. In turn, frailty describes a state in which physiologic reserve is depleted to the point that even small stressors can result in poor outcomes, including delirium, falls, disability and death.³ Markers of frailty are very common in older patients with hematologic malignancy—over half have evidence of malnutrition, and over a third have impaired physical function.⁴ Increased frailty in this population has been associated with increased chemotherapy-related toxicity, poor response to therapy, inability to complete planned course of therapy, and mortality.⁵ Accordingly, the National Comprehensive Cancer Network recommends the incorporation of frailty assessment into the routine care of older cancer patients.⁶

Frailty is a dynamic process that can worsen or improve over time. For example, elderly cancer patients who undergo inpatient geriatric assessment and management have been shown to become less frail, more likely to return home, and less likely to have cognitive or functional decline.⁷ Inpatient geriatric co-management has also been shown to substantially improve mood, social function and pain management post-discharge.⁸ A systematic review of geriatric evaluation and management of older adults with blood cancers found that non-oncologic interventions are implemented by geriatricians in over 70% of patients, most often targeting nutrition, mood, physical function, polypharmacy, and social function.⁴

While there are limited studies regarding geriatric co-management in the outpatient hematology setting, and no randomized controlled trials to determine the best model of

delivering such care, observational research is instructive. Elderly AML is an excellent example: our own work has shown that markers of frailty are independent prognostic factors for death in models that included cytogenetic risk group, even for those patients with good baseline performance status (ECOG 0-1).⁹ Given this context, we are interested in measuring the frailty of older adults with blood cancers with precision, determining how much it contributes to prognosis compared with clinical disease-specific measures and molecular markers, and determining if co-management by a geriatrician embedded in the oncology clinic can decrease frailty and improve disease-related outcomes.

Indeed, we have begun to see the increased burden of caring for elderly patients in hematologic oncology at Dana-Farber. During the period March 2013 to February 2014, for patients 75 and older, we had 3429 clinical visits in lymphoma (674 unique patients), 1704 for leukemia/related disorders (318 unique patients), and 3,245 for multiple myeloma (516 unique patients). Our older patient volume reflects an outstanding opportunity to both improve our care delivery and research the impact of frailty on disease outcomes. We wish to launch a research program to engage these patients in formal geriatric assessment and management, with the aim of addressing this important clinical and data gap.

2.2 *Frailty Assessment*

There are many frailty models, but two of the most commonly used models are the phenotype model and the cumulative deficit model.¹⁰ The phenotype model is a categorical model that uses 5 separate variables to identify frailty. The variables are interrelated and are indicative of decreased physiologic reserve and resistance to stressors, two conditions that constitute the clinical definition of frailty.³ The phenotype model is also popular because of its clinical reproducibility.¹¹ The cumulative deficit model is a continuous model of frailty that uses assessment of a large index of symptoms to determine frailty status,^{10,12} with a higher number of symptoms leading to a greater likelihood of being frail.^{10,13} The cumulative deficit model is popular because it can evaluate impairments in many biological systems, is graded, and is conceptually simple.¹³

Rockwood and Mitnitski created a standard cumulative deficit approach with their Comprehensive Geriatric Assessment (CGA), with approximately 40 variables, some of which are self-reported (e.g. “how would you rate your health?”), others are ascertained by tests such as the Montreal Cognitive Assessment (MoCA)¹⁴, and others are determined by clinical evaluation (e.g. high blood pressure).¹⁵ The efficacy of this model was examined by Searle et al. in a 2008 study, which analyzed a group of 754 community dwelling elderly people who were assessed and then longitudinally followed for outcomes.¹² The study found that the CGA was a significant predictor of mortality.

Sheppard et al. examined a cohort of 1,288 older women with breast cancer in order to validate use of this frailty index in a cancer population, aiming to assess its utility in predicting non-initiation or discontinuation of adjuvant hormonal therapy.¹⁶ The investigators used a 35-item index adapted from the Searle approach. The index included self-reported items relating to limitations in basic and instrumental activities of daily living, sensory deficits, functioning, and the pre-diagnosis of comorbidity. They did not include measures of cognitive impairment, because women with cognitive impairment were excluded.

After calculating frailty scores on the 0-1 scale, cut-points of 0-0.2 for “robust”, 0.2-0.35 for “pre-frail”, and 0.35-1.0 for “Frail” were used. The study found that both frailty and pre-

frailty were significantly related to non-initiation of therapy. Although a trend was cited for frailty or pre-frailty and discontinuation of therapy, after considering covariates, no significant relationship was demonstrated. These data suggest that the frailest women never initiated therapy, which may explain why a significant relationship between frailty and discontinuation was not observed.¹⁶ Sheppard concluded that although the results for frailty were suggestive, they should be confirmed in other studies of cancer populations. We will aim to apply this cumulative deficit assessment technique to DFCI's older hematologic oncology population.

The phenotype approach takes into account 5 factors that indicate frailty, including unintentional weight loss, self-reported exhaustion, low energy expenditure, slow gait speed, and weak grip strength. After evaluation, people with 3 or more of the factors are categorized as "frail", people with 1 or 2 factors are "pre-frail" and people with no factors are "robust".¹⁰ In a longitudinal study of community dwelling men and women aged 65 and older, Fried and associates found that people who were initially categorized as frail based on the phenotype model had more adverse outcomes at 3 and 5 year follow ups compared to people who were categorized as robust. Those who were found to be pre-frail at baseline exhibited outcome measures that fell intermediate between the other two groups.³ Our study will look to expand upon these results and validate the phenotype approach, in addition to the cumulative deficit approach above.

2.3 Potential Benefits

The clinical and research program we propose will involve formal geriatric assessment and management of older patients with hematologic malignancies. This will likely be of direct benefit to patients as geriatric assessment has been shown to improve functional status, decrease hospitalization, and even lengthen life in non-cancer populations. In addition, by providing these services in the setting of a randomized controlled trial, we will be able to assess the efficacy of geriatric co-management and determine which components are most valuable to improving patient outcomes. Our study will help to further validate frailty assessment as a tool for the evaluation of geriatric cancer patients. Finally, this project will generate a comprehensive database of clinical and disease-specific factors that will allow us to build models to predict prognosis and toxicity and provide pathologic samples of older patients with hematologic cancers for study in the laboratory. These data in turn will ultimately be used to individualize cancer therapy for older patients with hematologic cancers.

3.0 OBJECTIVES/STUDY AIMS

The goal of this study is to establish a research program – the Older Adult Hematologic Malignancy (OHM) program – that will address important gaps in data about how best to care for older adults with hematologic malignancies. It is clear that markers of frailty are important predictors of tolerance of therapy and survival, but few studies have assessed their value in this population. Geriatric assessment and co-management are associated with improvements in quality of life, resource utilization and survival, but have not been tested scientifically in hematologic malignancies. We therefore propose the following specific aims:

3.1 Specific Aim 1

Characterize the prognostic value of frailty as compared to clinical prognostic models for older patients with blood cancers. We will perform a combined frailty

assessment in patients 70 and older who present to DFCI with a new diagnosis of MDS or a hematologic malignancy. Patients will be categorized as robust, pre-frail or frail based on their frailty score. We will then determine how the presence or absence of frailty predicts important outcomes such as treatment, resource utilization and mortality. In a subset of patient who specifically agree, frailty will be re-assessed at subsequent visits.

Hypothesis: Frailty will predict survival for those older patients with low-risk disease on molecular markers/disease-based risk systems, but be trumped by these for patients with high-risk disease.

3.2 Specific Aim 2

Determine if co-management of frail and pre-frail older adults with blood cancers by an embedded geriatrician improves outcomes. Patients who score as pre-frail or frail will be randomized to geriatric assessment and co-management with a geriatrician or usual care. They will be followed for disease-specific outcomes, with the primary outcome being overall survival at 1 year.

[figure not shown]
Hypothesis: For those assessed to be frail with rigorous measurement, co-management by an embedded geriatrician will improve overall survival at one year.

4.0 ELIGIBILITY

All patients aged 70 and older who present for an initial consultation at the DFCI for MDS or a hematologic malignancy (transplantation consultation excluded) are eligible. Note that until September 2020, before virtual assessments, only patients aged 75 and older were eligible due to resource limitations; this has been changed to include patients aged 70 and older because we can now accommodate more patient assessments virtually. For Specific Aim 2, insurance information will be reviewed to ensure geriatric referral is covered for all potential participants. This step will allow us to avoid a situation arising wherein a participant is randomized to geriatric co-management, yet their insurance does not cover geriatrician visits. As baseline geriatric assessment by our research assistant and later randomization to co-management by a geriatrician are currently precious resources, in practicality, to be eligible, patients will have to present on one of the three days per week that geriatric assessments are available, and be willing to be seen for geriatric co-management on one of the two geriatrician clinic days.

5.0 STUDY DESIGN and PROCEDURES

Due to challenges presented by the ongoing COVID-19 pandemic and the specific vulnerability of the population we intend to study, we recognize the need to preserve the safety and comfort of the participating patients. For this reason, we propose an updated study design that allows the completion of remote, in-home frailty assessments that minimize exposure risk. This adapted workflow is illustrated below and described in the following sections.

5.1 Patient Selection and Recruitment

All eligible patients will be given an in-person or virtual appointment with our clinical research coordinator before their first meeting with their hematologist to discuss the study; the type of appointment will depend on availability during the COVID-19 pandemic. This CRC will have been trained in frailty assessment by [name] and will be responsible for obtaining informed consent and completing the baseline frailty assessment for patients who consent. Importantly, patients will be able to consent to the baseline assessment, a potential follow-up assessment at a future visit, and/or allowing collection of extra samples for the laboratory. Categorical frailty status (robust versus frail/pre-frail) will be emailed to clinicians.

For Specific Aim 2 (now closed to enrollment), patients will be allowed to see a geriatrician outside of the trial design if they ask for this or if their physician requests it. We acknowledge that this may somewhat affect our randomized design, however, we feel that it is important to offer this service. Frail or pre-frail patients who were not randomized to geriatric co-management but who see a geriatrician anyway will first be analyzed in an intent-to-treat manner and then excluded from a secondary analysis to assess if this event affects overall findings.

As above, frail, pre-frail and robust patients will undergo additional prospective evaluation to assess for study outcomes: for Specific Aim 1 we will compare frail and pre-frail

patients who did not see a geriatrician to robust patients, and for Specific Aim 2, we will compare frail and pre-frail patients who saw a geriatrician to those who did not (see schema).

For all patients who go on to see a geriatrician, whether inside or outside of the trial design, continued follow-up (i.e. past the initial comprehensive geriatric assessment) will be determined by discussion between the geriatrician, the patient, and the patient's DFCI oncologist. As long as this resource remains available, patients will be able to follow-up with our geriatricians as long as they continue to receive their care at DFCI.

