6.3 Power Considerations

Power analysis is based on Specific Aim 2, as the patients enrolled therein will be a subset of the patients from Specific Aim 1. The study is powered to detect a difference in the one-year overall survival rate (i.e., the primary endpoint) between the two groups in Specific Aim 2: those patients who see a geriatrician (Group 2) and those who do not (Group 1). Based on prior observational data, overall survival in Group 1 is expected to be 68% at one year (this is based on the one-year OS of a sample of 114 MDS patients followed at DFCI from 2006 to 2012). We expect the one-year overall survival rate in Group 2 (the intervention group) to be 85%, which corresponds a 25% of improvement over Group 1. A total sample size of 160 (107 Group 1; 53 Group 2) would achieve 80% power to detect this difference, at 0.05 one-sided type I error level.

Indeed, the number of patients seen in the OHM program will be limited by the resources of the CRC and the geriatricians. In one year, given current numbers, we would expect 600 unique myeloma, lymphoma and AML/MDS patients over aged 75 (see above) to present at DFCI. We will be aiming to undertake baseline assessments for all new patients appearing on four calendar days each week. We originally hoped to have 540 potential patients for Specific Aim 1. As of December 18, 2017, 494 patients out of the 570 patients approached (87%) have agreed to Specific Aim 1. Given our line of success with enrolling patients since February 3, 2015, and after discussions with our clinicians, we hope to recruit three times the number of

patients originally planned for this aim in order to conduct disease-specific analyses. We hope to have 1,620 potential patients for Specific Aim 1 so we may stratify analyses by our three disease-specific clinics at DFCI (MDS/leukemia, lymphoma, and myeloma).

If 216 (60%) of the 540 patients, originally planned for accrual, are ultimately assessed by the CRC, and 25% found to be frail or pre-frail continue to receive care at DFCI, and agree to the RCT, this leaves 54 to be randomized to geriatric co-management vs. routine oncology care (27 in each group) per year. Our hope is to reach a sample size of 160 patients (107 Group 1; 53 Group 2) for Specific Aim 2 in three years, but we will extend the study until we achieve this enrollment. Of note, we have expanded our geriatrician clinics to two sessions per week to accommodate this increased patient load.

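### Aim 2: excluding usual-care patients who see a geriatrician cannot show whether crossover affected the result, because the exclusion itself can shift control survival in either direction

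*Combined protocol and SAP*

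**What the plan says.** Section 5.1 opens a route to crossover in Aim 2: "patients will be allowed to see a geriatrician outside of the trial design if they ask for this or if their physician requests it". The same section has frailty status sent to the treating clinicians ("Categorical frailty status (robust versus frail/pre-frail) will be emailed to clinicians"), so a physician request can follow from the trial's own assessment.

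Frail or pre-frail "patients who were not randomized to geriatric co-management but who see a geriatrician anyway" are handled in two steps. They "will first be analyzed in an intent-to-treat manner and then excluded from a secondary analysis to assess if this event affects overall findings". The rule names only patients not assigned to co-management; no matching rule covers co-management patients who never attend. Neither 5.1 nor 6.2 gives a time window, landmark, censoring rule or weighting. Section 6.2 adjusts for age, gender, race-ethnicity and disease type.

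The endpoint at issue is survival: section 3.2 describes Aim 2 "with the primary outcome being overall survival at 1 year", and section 6.3 assumes that "overall survival in Group 1 is expected to be 68% at one year". No section states an expected crossover rate or when crossover visits would occur.

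**The concern.** The secondary analysis has one stated purpose: to show whether off-design visits changed the findings. It removes controls on the basis of something that happens after randomisation, and this disturbs the comparison in two ways.

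- **Survival to the visit.** Only a living patient can see a geriatrician. A control who dies early can never be removed, while every removed control survived at least to the visit. Taken alone, this lowers survival among the controls who remain.
- **Selection by request.** Patients who ask, or whose physicians ask for them, may have a better or worse prognosis than other controls. Removing them leaves a control group that is no longer the randomised one. Adjustment for the four baseline covariates in 6.2 does not restore it.

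At stake is the interpretation. If the effect grows after the exclusion, the natural reading is that contamination had diluted a real benefit. If it shrinks or stays put, the natural reading is that contamination did not matter. Either pattern can come from the exclusion alone.

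**Working it through.** **Inputs.** From section 6.3: one-year survival of 68% in controls and 85% with co-management; 107 and 53 patients; one-sided 0.05; stated power 80%. Assumed, because the documents are silent: constant hazard, crossover rate, crossover timing, and any link between crossover and prognosis.

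**Plan's own figure.** The unpooled standard error is √(0.68×0.32/107 + 0.85×0.15/53) = 0.0666. Then 0.17/0.0666 = 2.55, and Φ(2.55 − 1.645) = 81.8%, close to the stated 80%. The inputs are used as the plan means them.

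**Step 1: no treatment effect, switching unrelated to prognosis, spread over the year.** The death hazard is λ = −ln 0.68 = 0.386 per year. With switching hazard μ:

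- alive at one year and never switched: e^−(λ+μ)
- retained (never switched): e^−(λ+μ) + [λ/(λ+μ)]·[1 − e^−(λ+μ)]
- retained-control survival: the first divided by the second

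| μ per year | Controls who switch | Retained-control survival | Spurious benefit (points) | Survival of switchers |
|---|---|---|---|---|
| 0.10 | 7.9% | 0.6153/0.9208 = 66.8% | 1.2 | 81.7% |
| 0.20 | 15.1% | 0.5567/0.8486 = 65.6% | 2.4 | 81.4% |
| 0.35 | 24.8% | 0.4792/0.7522 = 63.7% | 4.3 | 81.0% |

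The true value is 68% in every row.

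**Step 2: all visits at one time t.** If a fraction q would switch at t and is removed only if alive then, retained-control survival is 0.68(1−q)/(1−q·S(t)), with S(t) = 0.68^t.

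| Visit time | S(t) | Bias, q = 10% (points) | Bias, q = 20% (points) | Bias, q = 30% (points) |
|---|---|---|---|---|
| 1 month | 0.968 | 0.2 | 0.5 | 0.9 |
| 3 months | 0.908 | 0.7 | 1.5 | 2.6 |
| 6 months | 0.825 | 1.3 | 2.9 | 4.8 |

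For example, at q = 20% and 6 months: 0.544/(1 − 0.165) = 65.1%. In simulation with 107 and 53 patients and q = 20%, the one-sided false-positive rate of the excluded-control comparison is about 0.058, 0.070 and 0.099 for visits at 1, 3 and 6 months, against a nominal 0.05.

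**Step 3: let the switchers be sicker.** Keep overall control survival at 68%, set q = 20%, and give would-be switchers k times the death hazard of other controls. Choose the others' hazard λ₀ so that 0.8e^(−λ₀) + 0.2e^(−kλ₀) = 0.68. Retained-control survival is 0.8e^(−λ₀)/(1 − 0.2A), where A is the average chance that a would-be switcher is alive at the visit. A positive bias favours co-management.

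| Hazard ratio k | Bias, visits over 0–3 months (points) | Bias, visits over 0–6 months (points) |
|---|---|---|
| 1.0 | +0.8 | +1.5 |
| 1.25 | −0.3 | +0.6 |
| 1.5 | −1.2 | −0.2 |
| 2.0 | −2.7 | −1.5 |
| 3.0 | −4.8 | −3.2 |

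For example, k = 2 with visits over 0–6 months: λ₀ = 0.328, e^(−λ₀) = 0.720, A = 0.853, so 0.576/0.829 = 69.5%. At q = 20% the sign changes at a hazard ratio of about 1.2 (visits over 0–3 months) or 1.4 (visits over 0–6 months).

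**Step 4: the replacement under the same null.** The complier-average effect is (difference in one-year survival by randomised arm)/(p₁ − p₀), where p₁ and p₀ are the proportions in each arm who saw a geriatrician. Nobody is removed, so with no treatment effect the numerator centres on zero whoever switches and whenever they do.

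**The case against.** Several points on the other side stand.

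- **Direction.** A reader might infer that the exclusion necessarily lowers control survival and flatters co-management. The documents do not support that. Section 5.1 ties switching to requests, and modestly sicker switchers reverse the sign (Step 3).
- **Primary result.** A reader might also infer that the primary conclusion is biased, the more so because 5.1 elsewhere says "we will compare frail and pre-frail patients who saw a geriatrician to those who did not", and 6.3 describes its groups in similar terms. But the crossover rule puts intent-to-treat first, and nothing lets the exclusion replace it. Section 5.1 also acknowledges that off-design visits may somewhat affect the randomised design.
- **Size.** The 1 to 4 points compare with a planned difference of 85 − 68 = 17 points. The standard error with 68% survival in both arms is √(0.68×0.32×(1/107 + 1/53)) = 7.8 points. Few or early switches would make the bias negligible.
- **Remedy.** Weighted censoring at the first visit needs prognostic data over time; section 5.4 describes record review at baseline and one year, with periodic survival checks. Table 3 lists no geriatrician visit date. A binary exposure counts a month-11 visit like an early one.
- **Timing.** Aim 2 is closed to enrolment, and section 8.0 schedules its analysis and manuscript to finish by January 2020.

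These limit the direction claimed, the consequence and the choice of method. They do not rescue the check. An unknown sign means that it cannot answer the question it was written for.

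**Conclusion.** The concern holds for the secondary analysis only. The exclusion is one-sided and conditions on a post-randomisation event, so it cannot separate contamination from selection or from survival to the visit. Survival to the visit alone yields about 1 to 4 points of spurious benefit at 8% to 25% switching over the year, and under 1 point if all switching (10% to 30% of controls) occurs at 1 month. These figures rest on 68% control survival, a constant hazard, no treatment effect and switching unrelated to prognosis. Prognosis-related requests can offset or reverse them. Without a stated switching rate or timing, neither the net sign nor the actual size can be derived from the documents. The intent-to-treat result is unaffected. This should be corrected, but it does not threaten the primary analysis as planned.

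**What to change.** In 5.1 and 6.2:

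1. State that intent-to-treat is the only confirmatory analysis of one-year survival.
2. Replace the exclusion with a complier-average causal effect on one-year survival, using randomised arm as the instrument and having seen a geriatrician as the exposure. Every randomised patient stays in the assigned arm.
3. Report the number and timing of crossovers, so that readers can judge how far late visits blur the exposure.
4. Make inverse-probability-weighted censoring at the first visit optional, only if the time-varying data it needs exist.

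If Aim 2 has already been analysed with the exclusion, add this estimate, or attach a caveat that a shift in the excluded-control result cannot be attributed to contamination.

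**Cost.** Wording and a modest analysis. The exclusion already requires knowing which controls saw a geriatrician; the same status is needed in the co-management arm, and visit dates would have to be taken from the medical record. The interval widens by roughly 1/(p₁ − p₀): with full attendance in the co-management arm and 15% crossover (both assumed), a standard error of 7.8 points becomes about 7.8/0.85 = 9.2. The estimate also assumes that assignment affects survival only through seeing a geriatrician, and it treats late and early visits alike.

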Emergency department visits	6 months	Number of ED visits	Patient medical record and outside records
Code status documentation	6 months	Code status entered into the medical record	Patient medical record
Continuation of care at DFCI	6 months	Number of visits and length of follow-up at DFCI; receipt of treatment at DFCI	Patient medical record
Δ Number of medications	Baseline to 3 months	Overall number of medications = number of cancer meds + number of non cancer meds	Patient medical record
Δ Blood pressure	Baseline, 6 months	Measured at each visit	Patient medical record
Content Analysis of Notes	6 months	Only patients randomized to geriatrician	Patient medical record

*primary outcome

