6.0 ANALYTIC CONSIDERATIONS

6.1 Specific Aim 1

We will first perform descriptive analyses of covariates of frailty/pre-frailty in our population, including age, gender, race-ethnicity, and disease type. Means and proportions will be used to describe patient characteristics, individual and summary frailty responses, baseline clinical data, and treatment assignment. We will identify variables that are associated with the outcomes of interest using Kaplan-Meier curves and log-rank tests. Given limited numbers of patients and other study resources, we will plan to combine the frail and pre-frail groups in our analyses for Aim 1 (frail/pre-frail versus robust), but if power allows, we will also compare outcomes for all three groups (frail versus pre-frail versus robust). We will use the tests above for univariate analyses to determine whether any of the relevant geriatric domains, socio-demographic factors, or clinical data are associated with choice of treatment, length of time in the hospital and survival. We will also perform univariable and multivariable analyses to determine if frailty interacts with other patient characteristics to influence outcomes. We will also conduct analyses specific to disease clinics at DFCI (MDS/leukemia versus lymphoma versus myeloma). We will consider a p value < 0.05 to be significant, and all analyses will be carried out using SAS v.9.

6.2 Specific Aim 2

For frail patients, pre-frail patients and the combined cohort, we will create multivariable models to assess the impact of geriatric co-management on the outcomes listed in Table 3, controlling for age, gender, race-ethnicity, and disease type. We will consider a p value < 0.05 to be significant, and all analyses will be carried out using SAS v.9. Of note, we again plan to combine the frail and pre-frail groups in our analysis given limited resources and lack of current data as to whether or not geriatric intervention is more helpful in one of these groups; if power allows (see below), we will also adjust for frail versus pre-frail status.

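### Sections 5.1 and 6.3 word the Aim 2 groups by whether patients saw a geriatrician, and no text keeps co-management patients who die or do not attend before a visit in their randomised arm

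*Combined protocol and SAP*

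**What the plan says.** **Aim 2.** Section 3.2 sets up a randomised comparison: "Patients who score as pre-frail or frail will be randomized to geriatric assessment and co-management with a geriatrician or usual care". Section 5.1 then words the comparison by attendance: "for Specific Aim 2, we will compare frail and pre-frail patients who saw a geriatrician to those who did not (see schema". Section 6.3, which powers the primary endpoint of one-year overall survival, describes the two groups as "those patients who see a geriatrician (Group 2) and those who do not (Group 1".

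The one intent-to-treat statement is in 5.1. It concerns frail or pre-frail patients who were not randomised to co-management but see a geriatrician anyway; they "will first be analyzed in an intent-to-treat manner and then excluded from a secondary analysis". Section 6.2 describes models for the effect of co-management without saying who is analysed in which group. Table 3 in section 5.4 does use assignment language for one outcome: "Only patients randomized to geriatrician". Section 4.0 requires patients to "be willing to be seen for geriatric co-management on one of the two geriatrician clinic days".

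**Aim 1.** Section 5.1 compares frail and pre-frail "patients who did not see a geriatrician to robust patients". Section 6.1 plans to "combine the frail and pre-frail groups in our analyses for Aim 1 (frail/pre-frail versus robust", with no condition about a geriatrician visit.

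**The concern.** Seeing a geriatrician happens after randomisation, and a patient must be alive for it to happen. If it defines the groups, a co-management patient who dies before the visit counts in Group 1. The time from randomisation to the visit is then immortal time for Group 2, and the resulting error favours the intervention on the primary endpoint. The willingness criterion in 4.0 reduces refusal, but it cannot prevent death before a visit.

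The intent-to-treat sentence points the other way from the attendance wording. It keeps usual-care crossovers in their arm, whereas the attendance wording would put them in Group 2. Section 5.1 is therefore inconsistent with itself, and the co-management arm is left without a rule.

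In Aim 1 the same kind of post-baseline event trims the frail/pre-frail group in 5.1 but not in 6.1, so the population of the prognostic comparison is unclear.

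**Working it through.** **Inputs from section 6.3.** One-year survival of 68% (Group 1) and 85% (Group 2), 107 and 53 patients, one-sided 5%, stated power 80%.

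**The plan's own figure.** Unpooled two-proportion z-test: SE = √(0.68×0.32/107 + 0.85×0.15/53) = 0.0666. Power = Φ(0.17/0.0666 − 1.645) = Φ(0.907) = 81.8%; exact enumeration of this test gives 80.2%. The stated 80% is reproduced. The pooled version gives 76.6%.

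**Aim 2 under the attendance wording, no true effect.** Assumptions, none of them in the documents:
- 68% one-year survival in both arms and a constant hazard, λ = −ln(0.68) = 0.386 per year.
- Visits spread evenly over the first w months, and every co-management patient alive at the visit attends.
- Usual-care crossovers stay in Group 1, as the intent-to-treat sentence says.

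With T = w/12:
- Share alive at the visit: a = (1 − e^(−λT))/(λT)
- Deaths moved to Group 1: 53(1 − a)
- Group 2 survival: 0.68/a
- Group 1 survival: 107×0.68/(107 + 53(1 − a))

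For w = 1: λT = 0.0321 and a = 0.984. Deaths moved = 0.84. Group 2 = 0.68/0.984 = 69.1%. Group 1 = 72.76/107.84 = 67.5%.

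| Visits over first | a | Deaths moved | Group 2 | Group 1 | Spurious gain (points) | One-sided error |
|---|---|---|---|---|---|---|
| 0.5 month | 0.992 | 0.4 | 68.5% | 67.7% | 0.8 | about 6% |
| 1 month | 0.984 | 0.8 | 69.1% | 67.5% | 1.6 | 7.5% |
| 2 months | 0.969 | 1.7 | 70.2% | 67.0% | 3.2 | 10.6% |
| 3 months | 0.953 | 2.5 | 71.3% | 66.5% | 4.9 | 14.9% |

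Gains are taken before rounding. The error column comes from 200,000 simulated trials per setting with a pooled z-test. Analysed by randomised arm, the same trials give no gain and an error of about 5%.

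**Sensitivity.**
- With 90% attendance unrelated to prognosis, the error for 1, 2 and 3 months is 7.2%, 10.0% and 13.5%.
- If all visits fell at a fixed 4, 8 or 12 weeks, the gain would be 3.0, 6.0 or 9.1 points and the error about 10%, 18% or 30%.
- Non-attendance unrelated to prognosis, with no early deaths, gives no bias.

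**Aim 1.** Suppose a share s of frail/pre-frail patients is seen and excluded, with visits unrelated to prognosis. The share assigned a visit is F = s/a, and survival in those never seen is (1 − F)×0.68/(1 − s). With s = 27% (assumed) and w = 1, F = 0.27/0.984 = 0.274 and survival is 0.726×0.68/0.73 = 67.6%, against 68%. The hazard is overstated by ln(0.676)/ln(0.68) − 1, about 2%. For w = 3, survival is 66.8% (about 5%). Only visits spread over the whole year give 62.8% (about 20%). With s = 10% the overstatements are about 0.5%, 1.4% and 6%.

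If everyone seen came from a sicker half (53% versus 83% one-year survival), excluding 27% would raise survival to 73.0% (w = 1) or 72.0% (w = 3), which reverses the direction.

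**The case against.** The strongest reply is that seeing a geriatrician is shorthand for the randomised arm. Section 6.3 itself labels Group 2 as the intervention group, uses the 107 and 53 as an enrolment target, and speaks of patients being randomised to co-management. An enrolment target can be set by arm, but not by later attendance. Table 3 also uses assignment language, and the 5.1 sentence refers to a schema that is not shown in the available text. Naming intent-to-treat first for crossovers suggests the same principle was meant throughout. This stands as evidence of intent. It does not supply the missing rule for co-management patients who are never seen.

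A reader might infer that the plan prescribes an as-treated primary analysis, or that the Aim 2 result is biased. The documents support neither: the wording conflicts with itself, and nothing shows which grouping was used.

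The calculation is also a hybrid, with usual-care patients kept by arm and co-management patients grouped by attendance. That combination follows from applying the intent-to-treat sentence only where it reaches. Its size depends wholly on assumed visit timing.

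On Aim 1, section 5.3 makes only patients who score frail or pre-frail eligible for geriatrician evaluation, so a limit on that side alone largely follows from the design. If the phrase again means assignment, little is wrong. A reader might infer that Aim 1 materially overstates the effect of frailty; the figures do not support that for early visits, and the sign depends on who is referred.

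**Conclusion.** The point holds as a defect in the written plan: the primary comparison is worded by a post-randomisation event in two places, and no available text protects the co-management arm against reclassification of early deaths. The arms were probably what was meant, so confidence that the analysis itself was affected is limited.

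The bias estimate applies only if the attendance wording was followed, and it rests on a constant hazard and the assumed visit windows. Within those, it is large enough to matter for a trial testing at a one-sided 5%.

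The Aim 1 discrepancy is secondary. It needs reconciling for clarity, not because a material bias has been shown.

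**What to change.** **Aim 2.** In 5.1 and 6.3, define Groups 1 and 2 by randomised assignment. In 6.2, state that the primary analysis includes all randomised patients in their assigned arm, including co-management patients who die or do not attend before a visit. Label the exclusion of usual-care crossovers as a sensitivity analysis. Section 5.1 says that Aim 2 is closed to enrolment, and the timeline in 8.0 places its final manuscript between September 2019 and January 2020. The practical step is therefore to state which grouping was used, and to reanalyse by arm only if patients were grouped as seen.

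**Aim 1.** Make 5.1 and 6.1 agree. Group by baseline frailty, and either adjust for randomised arm or exclude only patients randomised to co-management; do not exclude on an actual visit.

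**Cost.** A few sentences and modest analysis work. Non-attendance dilutes the effect by arm. If 90% attend (assumed) and non-attenders gain nothing, Group 2 survival is 0.85 − 0.10×0.17 = 83.3% and the difference falls from 17 to 15.3 points. Power falls by about 9 points: 82% to 72% unpooled, or 77% to 67% pooled. Grouping by attendance would not be a valid way to recover that power.
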